13.4 Appendix IV: Exercise Tolerance Testing Procedures

Subjects confirmed by the ECL to meet the AS criteria should undergo ETT unless contraindicated. A symptom-limited exercise test with the goal of reaching 80% to 85% of the age-predicted maximum heart rate is recommended. The recommended protocol is the modified-Bruce with treadmill, however the choice of the specific ETT protocol for each subject is per the clinical judgment of site study team.

During the test, subjects should be questioned for symptoms every 2 min, and blood pressure and a 12-lead ECG are recorded at baseline, at the end of each stage, and at peak exercise. The test should be stopped prematurely for symptoms (significant breathlessness) or any chest constriction or dizziness), progressive ventricular ectopy >3 beats, new atrial fibrillation, a sustained fall in systolic blood pressure >10 mm Hg from the previous stage or more than 2 mm ST segment depression.³⁹ Significant breathlessness can be differentiated clinically from physiological breathlessness by the presence of distress, the inability to speak, facial pallor and sometimes associated ventricular ectopy or a fall in blood pressure.⁸⁴

The following information should be recorded: reason(s) for stopping (symptom, fall in blood pressure, ventricular ectopy, ST segment depression and fatigue with physiological breathlessness), exercise time, exercise capacity in metabolic equivalents (METs), maximum rise in systolic blood pressure and maximum fall from peak and ST segment depression in millimeters, and percentage of target heart rate achieved.

METs should be calculated from the speed and gradient of the treadmill by the machine's software using the formula $(\text{METs} = [(\text{speed} \times 0.1) + (\text{gradient}/100 \times 1.8 \times \text{speed}) + 3.5]/3.5)$, where speed is measured in meters/minute and grade as a percentage. One MET is usually defined as the energy expended at rest, which is equal to a body oxygen consumption of nearly 3.5 mL per kilogram of body weight for an average adult.⁸⁵

A positive ETT is defined by the development of significant symptoms, a sustained fall in systolic blood pressure >10 mm Hg below baseline or more than 2 mm ST segment depression, a sustained tachyarrhythmia, or test limiting dyspnea or fatigue before reaching 60% age and gender adjusted predicted MET capacity. At maximum, up to 30 subjects with a positive ETT will be included in the study. Subjects with a positive ETT may continue in the study until the 30-subject maximum is reached. Once the 30-subject maximum is reached, only subjects with a negative ETT may continue in the study.

13.5 Appendix V: Cardiac Magnetic Resonance Imaging (CMR) Procedures

Subjects confirmed by the ECL to meet the AS criteria should undergo CMR with late gadolinium enhancement (LGE) unless contraindicated, and subjects implanted should have a CMR at the six-month follow-up. CMR exams can be performed with either 1.5 Tesla or 3 Tesla. Details of the acquisition protocol will be provided under separate cover. CMR exams will be sent to a core CMR lab for centralized analysis. The following variables will be reported:

- Left ventricular end-diastolic volume
- Left ventricular end-systolic volume
- Left ventricular end-diastolic volume index
- Left ventricular end-systolic volume index
- Left ventricular ejection fraction
- Stroke volume
- Stroke volume index
- Left ventricular mass
- Left ventricular mass index
- Maximum left ventricular wall thickness
- Left ventricular mass/left ventricular volume
- Longitudinal systolic function
- Left atrial volume index
- Presence of infarct on LGE
- Infarct LGE mass
- Presence of midwall LGE
- Midwall LGE mass
- Aortic regurgitant volume (post implant only)
- Aortic regurgitant fraction (post implant only)

13.6 Appendix VI: Six Minute Walk Test (6MWT) Procedures

Subjects confirmed by the ECL to meet the AS criteria should have a 6MWT unless contraindicated, and subjects implanted should have a 6MWT at the six-month follow-up. The 6MWT test is administered per the site's standard procedure, although the following recommendations are intended to standard the test across sites and minimize sources of variability.⁸⁶

Technical Aspects. The 6MWT should be performed indoors, along a long, flat, straight, enclosed corridor with a hard surface that is seldom traveled. The walking course should be 30 meters in length, and the course marked every 3 meters. Turnaround points should be marked (e.g. with an orange traffic cone). A starting line, which marks the beginning and end of each 60-meter lap, should be marked on the floor using brightly colored tape. A stopwatch and means to record the number of laps should be in place (e.g. lap counter or worksheet).

Patient Preparation. Subjects should wear comfortable clothing and appropriate walking shoes; and should not have exercised vigorously within 2 hours of beginning the test. A light meal is acceptable before early morning or early afternoon tests. Patients should use their usual walking aids during the test (cane, walker, etc).

Test Procedures

1. Repeat testing should be performed about the same time of day to minimize intraday variability.
2. A "warm-up" period before the test should not be performed.
3. The subject should sit at rest in a chair, located near the starting position, for at least 10 minutes before the test starts.
4. Set the timer to 6 minutes and lap counter to zero (if used).
5. Instruct the patient as follows:

"The object of this test is to walk as far as possible for 6 minutes. You will walk back and forth in this hallway. Six minutes is a long time to walk, so you will be exerting yourself. You will probably get out of breath or become exhausted. You are permitted to slow down, to stop, and to rest as necessary. You may lean against the wall while resting, but resume walking as soon as you are able. Remember that the object is to walk AS FAR AS POSSIBLE for 6 minutes, but don't run or jog.

6. Position the patient at the starting line. As soon as the subject starts to walk, start the timer. Do not walk with the subject.

Use an even tone of voice when using standard phrases of encouragement. For example, after each minute tell the subject *"You are doing well and have X minutes to go"*. Do not use other words of encouragement (or body language to speed up).

[figure not shown]
If the subject stops walking during the test and needs to rest, do not stop the timer. The subject should be told to rest, *“but continue walking whenever you feel able.”* If the patient stops before the 6 minutes are up and refuses to continue (or you decide that they should not continue), bring a chair over for the patient to sit on, discontinue the walk, and note on the worksheet the distance, the time stopped, and the reason for stopping prematurely.

When the timer is 15 seconds from completion, tell the subject *“In a moment I’m going to tell you to stop. When I do, just stop right where you are and I will come to you.”* When the timer rings, mark the spot where they stopped walking.

7. Record the number of laps from the counter (or tick marks on the worksheet).
8. Record the additional distance covered (the number of meters in the final partial lap) using the markers on the wall as distance guides. Calculate the total distance walked, rounding to the nearest meter, and record on the worksheet.

13.7 Appendix VII: TAVR Implant Procedure

The implantation procedure is performed according to the standard procedures of the implanting physicians. Valve deployment in accordance with the cusp overlap technique⁶² is recommended for TAVR implant for all study subjects, as appropriate. Transfemoral access is required for the TAVR implant. For sites in the United States, the local heart team’s interventional cardiologist(s) and cardiac surgeon(s) must jointly participate in the intra-operative technical aspects of the TAVR procedure. Procedural aspects specific to the Medtronic TAVR system should be performed according to the Instructions for Use. TAV size selection should be based on MDCT measurements and the dimensional criteria shown in Figure 21.

Size	23 mm	26 mm	29 mm	34 mm
Annular perimeter	56.5 – 62.8 mm	62.8 – 72.3 mm	72.3 – 81.7 mm	81.7 – 94.2 mm
Annular diameter (mean)	18 – 20 mm	20 – 23 mm	23 – 26 mm	26 – 30 mm
Sinus of Valsalva diameter (mean)	≥ 25 mm	≥ 27 mm	≥ 29 mm	≥ 31 mm
Sinus of Valsalva height (mean)	≥ 15 mm	≥ 15 mm	≥ 15 mm	≥ 16 mm

Figure 21. TAV sizing matrix showing the anatomical dimensional criteria for each TAV size.

The following variables will be collected regarding the TAVR implantation procedure:

- Name of the primary operator
- Anesthesia type (general or local)
- Pre-implant pressures (LV systolic and end-diastolic, aortic systolic and diastolic)
- Pre-implant mean aortic gradient (simultaneous recording or LV and central aortic pressures)
- Pre-deployment BAV (yes/no)
- Use of rapid or controlled pacing during BAV and deployment (yes/no)

- Size of TAV implanted
- Post-implant dilation (yes/no)
- Implantation of TAV within the desired location (yes/no)
- Post-implant grade of prosthetic regurgitation by angiography (final result)
- More than one TAV implanted (yes/no)
- Patency of coronary arteries post-implant (yes/no)
- Occurrence of adverse events
- If TAV implantation not attempted, reason why

Criteria for grading prosthetic regurgitation by aortography⁸⁷

Grade 1+, mild: A small amount of contrast material enters the left ventricle in diastole; it is essentially cleared with each beat and never fills the ventricular chamber.

Grade 2+, moderate: More contrast material enters with each diastole and faint opacification of the entire chamber occurs.

Grade 3+, moderately severe: The left ventricle chamber is well opacified and equal in density with the ascending aorta.

Grade 4+, severe: Complete, dense opacification of the left ventricle chamber in one beat and the left ventricle appears more densely opacified than the ascending aorta.

13.8 Appendix VIII: Definitions of Endpoints and Outcome Measures

Definitions of safety endpoints, TAVR related complications, and efficacy endpoints are provided in Sections 13.8.1, 13.8.2, and 13.8.3, respectively. The CEC will code safety endpoints according to these definitions.

13.8.1 Safety Endpoint Definitions⁶³

Mortality

Cardiovascular: Any of the following:

- 1) Death due to proximate cardiac cause (eg, myocardial infarction, cardiac tamponade, worsening heart failure)
- 2) Death caused by non-coronary vascular conditions such as neurological events, pulmonary embolism, ruptured aortic aneurysm, dissecting aneurysm, or other vascular disease
- 3) All procedure-related deaths, including those related to a complication of the procedure or treatment for a complication of the procedure
- 4) All valve-related deaths including structural or nonstructural valve dysfunction or other valve-related adverse events
- 5) Sudden or unwitnessed death
- 6) Death of unknown cause

Non-cardiovascular: Any death in which the primary cause of death is clearly related to another condition (e.g., trauma, cancer, suicide).

Myocardial Infarction

Periprocedural MI (≤ 72 h after the index procedure): New ischemic symptoms (e.g., chest pain or shortness of breath), or new ischemic signs (e.g., ventricular arrhythmias, new or worsening heart failure, new ST-segment changes, hemodynamic instability, new pathological Q-waves in at least 2 contiguous leads, imaging evidence of new loss of viable myocardium or new wall motion abnormality) AND Elevated cardiac biomarkers (preferable CK-MB) within 72 h after the index procedure, consisting of at least 1 sample post procedure with a peak value exceeding 15x as the upper reference limit for troponin or 5x for CK-MB. If cardiac biomarkers are increased at baseline (>99 th percentile), a further increase in at least 50% post procedure is required AND the peak value must exceed the previously stated limit.

Spontaneous MI (>72 h after the index procedure): Any of the following criteria:

- 1) Detection of rise and/or fall of cardiac biomarkers (preferably troponin) with at least 1 value above the 99th percentile URL, together with the evidence of myocardial ischemia with at least 1 of the following:
 - Symptoms of ischemia
 - ECG changes indicative of new ischemia [new ST-T changes or new left bundle branch block (LBBB)]
 - New pathological Q-waves in at least 2 contiguous leads
 - Imaging evidence of a new loss of viable myocardium or new wall motion abnormality
- 2) Sudden, unexpected cardiac death, involving cardiac arrest, often with symptoms suggestive of myocardial ischemia, and accompanied by presumably new ST elevation, OR new LBBB, and/or evidence of fresh thrombus by coronary angiography and/or at autopsy, but death occurring before blood samples could be obtained, or at a time before the appearance of cardiac biomarkers in the blood.
- 3) Pathological findings of an acute myocardial infarction

Stroke and TIA

Diagnostic Criteria: Acute episode of a focal or global neurological deficit with at least 1 of the following:

- change in the level of consciousness
- hemiplegia, hemiparesis
- numbness or sensory loss affecting 1 side of the body
- dysphasia or aphasia
- hemianopia
- amaurosis fugax

1. other neurological signs or symptoms consistent with stroke
Stroke: duration of a focal or global neurological deficit ≥ 24 h; OR < 24 h if available neuroimaging documents a new hemorrhage or infarct; **OR** the neurological deficit results in death
TIA: duration of a focal or global neurological deficit < 24 h, any variable neuroimaging does not demonstrate a new hemorrhage or infarct
- 2) No other readily identifiable non-stroke cause for the clinical presentation (e.g. brain tumor, trauma, infection, hypoglycemia, peripheral lesion, pharmacological influences), to be determined by or in conjunction with the designated neurologist
- 3) Confirmation of the diagnosis by at least 1 of the following:
 - Neurologist or neurosurgical specialist, **OR**
 - Neuroimaging procedure (CT scan or brain MRI), but stroke may be diagnosed on clinical grounds alone

Stroke Definitions

Disabling stroke: mRS of 2 or more at 90 days and an increase in at least 1 mRS category from an individual's pre-stroke baseline

Non-disabling stroke: mRS of < 2 at 90 days or one that does not result in an increase in at least 1 mRS category from an individual's pre-stroke baseline

Stroke Classifications

Ischemic: an acute episode of focal cerebral, spinal, or retinal dysfunction caused by infarction of the central nervous system tissue

Hemorrhagic: an acute episode of focal or global cerebral or spinal dysfunction caused by intraparenchymal, intraventricular, or subarachnoid hemorrhage

Undetermined: insufficient information to allow categorization as ischemic or hemorrhagic

Bleeding Complications

Life-threatening or disabling bleeding: Fatal bleeding (*BARC type 5*) **OR**, bleeding in a critical organ, such as intracranial, intraspinal, intraocular, or pericardial necessitating pericardiocentesis, or intramuscular with compartment syndrome (*BARC type 3b and 3c*) **OR**, bleeding causing hypovolemic shock or severe hypotension requiring vasopressors or surgery (*BARC type 3b*) **OR**, overt source of bleeding with drop in hemoglobin ≥ 5 g/dL or whole blood or packed red blood cells (RBCs) transfusion ≥ 4 units¹⁰ (*BARC type 3b*)⁸⁸

Major Bleeding: Overt bleeding either associated with a drop in the hemoglobin level of at least 3.0 g/dL or requiring transfusion of 2 or 3 units of whole blood/RBC, **OR** causing hospitalization or permanent injury, **OR** requiring surgery **AND** does not meet criteria of life-threatening or disabling bleeding.

Minor bleeding: Any bleeding worthy of clinical mention (eg, access site hematoma) that does not qualify as life-threatening, disabling, or major.

Acute Kidney Injury (up to 7 days post procedure)

Stage 1: Increase in serum creatinine to 150%-199% (1.5-1.99 x increase compared with baseline) **OR**, increase of ≥ 0.3 mg/dL (≥ 26.4 mmol/L) **OR**, Urine output < 0.5 mL/kg/h for > 6 but < 12 h

Stage 2: Increase in serum creatinine to 200%-299% (2.0%-2.99% increase compared with baseline) **OR**, Urine output < 0.5 mL/kg/h for ≥ 12 but < 24 h

Stage 3: Increase in serum creatinine to $\geq 300\%$ (> 3 x increase compared with baseline) **OR**, serum creatinine of ≥ 4.0 mg/dL (≥ 354 mmol/L) with an acute increase of at least 0.5 mg/dL (44 mmol/L) **OR**, urine output < 0.3 ml/kg/h for ≥ 24 h **OR**, anuria for ≥ 12 h

¹⁰ Given one unit of packed RBC typically will raise hemoglobin concentration by 1 g/dL, an estimated decrease in hemoglobin will be calculated. A bleeding complication has to be the result of overt bleeding and cannot be adjudicated based on blood transfusions alone.

Vascular Access Site and Access Related Complications

Major vascular complication:

- 1) Any aortic dissection, aortic rupture, annulus rupture, left ventricle perforation, or new apical aneurysm/pseudoaneurysm **OR**,
- 2) Access site or access-related vascular injury (dissection, stenosis, perforation, rupture, arterio-venous fistula, pseudoaneurysm, hematoma, irreversible nerve injury, compartment syndrome, percutaneous closure device failure) *leading to death, life-threatening or major bleeding, visceral ischemia, or neurological impairment* **OR**,
- 3) Distal embolization (noncerebral) from a vascular source requiring surgery or resulting in amputation or irreversible end-organ damage **OR**,
- 4) Use of unplanned endovascular or surgical intervention associated with death, major bleeding, visceral ischemia or neurological impairment **OR**,
- 5) Any new ipsilateral lower extremity ischemia documented by patient symptoms, physical exam, and/or decreased or absent blood flow on lower extremity angiogram **OR**,
- 6) Surgery for access site-related nerve injury **OR**,
- 7) Permanent access-site related nerve injury

Minor vascular complication

- 1) Access site or access-related vascular injury (dissection, stenosis, perforation, rupture, arterio-venous fistula, pseudoaneurysms, hematomas, percutaneous closure device failure) *not leading to death, life-threatening or major bleeding¹¹, visceral ischemia, or neurological impairment* **OR**,
- 2) Distal embolization treated with embolectomy and/or thrombectomy and not resulting in amputation or irreversible end-organ damage **OR**,
- 3) Any unplanned endovascular stenting or unplanned surgical intervention not meeting the criteria for a major vascular complication **OR**,
- 4) Vascular repair or the need for vascular repair (via surgery, ultrasound-guided compression, transcatheter embolization, or stent-graft)

Percutaneous closure device failure: Failure of a closure device to achieve hemostasis at the arteriotomy site leading to alternative treatment (other than manual compression or adjunctive endovascular ballooning)

Valve Dysfunction Requiring Repeat Procedure: Any valve dysfunction that requires repeat procedure (e.g. balloon valvuloplasty, TAVR, snare repositioning, placement of vascular plug paravalvular leak, or surgical AVR)

¹¹ Refer to bleeding definitions

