2 Years (between 730 to 760 days post implant)

- Clinical assessment, including NYHA classification
- TTE
- Medications
- KCCQ
- Adverse events and device deficiencies

3 Years (between 1095 to 1125 days post implant)

- Clinical assessment, including NYHA classification
- TTE
- Medications
- KCCQ
- Adverse events and device deficiencies

4 Years (between 1460 to 1490 days post implant)

- Clinical assessment, including NYHA classification
- TTE
- Medications

- KCCQ
- Adverse events and device deficiencies

5 Years (between 1825 to 1855 days post implant)

- Clinical assessment, including NYHA classification
- TTE
- Medications
- KCCQ
- Adverse events and device deficiencies

Other Evaluations

- Suspected stroke events should be confirmed by neurology consult and neuroimaging per site’s standard practice. A Modified Rankin Score assessment should be conducted at 1 and 3 months following any confirmed stroke event.
- The investigative team should follow their standard practices for assessment of suspected myocardial infarction, acute kidney injury, neurological events, prosthetic valve endocarditis, prosthetic valve thrombosis, etc.
- Non-protocol echocardiograms (e.g. performed for suspicion of prosthetic valve dysfunction) should be submitted to the ECL for evaluation.

Table 1. Summary of required evaluations and visit schedule

	Baseline	Implant	Discharge	30 Days	6 Months	Annual through 5 Years	1 month post stroke event	3 months post stroke event
Clinical assessment including NYHA	✓ ⁵		✓ ¹	✓	✓	✓		
Transthoracic Echo	✓		✓ ⁴	✓	✓	✓		
Multi-detector CT	✓							
12-lead ECG	✓		✓	✓	✓			
Coronary arteriography	✓							
Exercise Tolerance Test (unless contraindicated)	✓							
Cardiac MRI	✓				✓			
6-Minute Walk Test	✓				✓			
Spirometry	✓							
Complete Blood Count	✓							
Pro B-type natriuretic peptide	✓				✓			

Heart Team Assessment	✓							
Aortography		✓						
Hemodynamics		✓						
Medications	✓		✓	✓	✓	✓		
KCCQ	✓			✓	✓	✓		
EQ-5D	✓				✓			
Modified Rankin Score	✓						✓	✓
Adverse Events and/or device deficiencies ²	✓	✓	✓	✓	✓	✓		

Notes

1. NYHA not required at discharge
2. Adverse events should be assessed and captured at each follow-up visit after time of informed consent.
3. Discharge TTE used for “Device Success” should be performed > 12 hours and ≤ 7 days post implant
4. Clinical assessment and medical history required at baseline

Visit Windows

Baseline	Within 12 weeks prior to submission to ERC (except for MDCT and coronary arteriography)

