7.9 Evaluation of Objectives

7.9.1 Safety Endpoints

The following safety endpoints are defined and will be analyzed:

1. All-cause and cardiovascular mortality at 30 days and 6 months
2. All stroke (disabling and non-disabling) at 30 days and 6 months
3. Myocardial infarction (periprocedural and spontaneous) at 30 days and 6 months
4. Acute kidney injury at 30 days and 6 months
5. Major vascular complications at 30 days and 6 months
6. Life-threatening bleed at 30 days and 6 months
7. New permanent pacemaker implantation (PPI) at 30 days and 6 months
8. New intraventricular conduction delays at 30 days and 6 months
9. New-onset atrial fibrillation at 30 days and 6 months
10. Valve-related dysfunction requiring repeat procedure at 30 days and 6 months

Safety endpoints will be adjudicated by the Clinical Events Committee (CEC) and analysis will be based on data collected on the CEC adjudication form. Safety endpoints will be analyzed with Kaplan-Meier survival analysis methods according to Section 7.2. Safety endpoints will be analyzed using the Attempted Implant population.

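### The acute kidney injury definition contradicts itself on units and on stage 2, and no creatinine is scheduled, so AKI may be under-ascertained and inconsistently classified

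*Protocol*

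**What the plan says.** Protocol Sections 4.2.1 and 10.4 list AKI among ten safety endpoints, without limiting it by stage. SAP Section 7.9.1 carries it over as "Acute kidney injury at 30 days and 6 months" and gives no definition of its own. Protocol Section 13.8 directs the CEC to code safety endpoints by the definitions that follow it, so Section 13.8.1 is the operative text.

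Its AKI heading sets the window: "Acute Kidney Injury (up to 7 days post procedure". Each stage can be met by a creatinine criterion or by a urine-output criterion. The creatinine criteria include:

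- Stage 1: "Increase in serum creatinine to 150%-199% (1.5-1.99 x increase compared with baseline", or an "increase of ≥ 0.3 mg/dL (≥ 26.4 mmol/L".
- Stage 2: "Increase in serum creatinine to 200%-299% (2.0%-2.99% increase compared with baseline".
- Stage 3: at least 300% of baseline, or "serum creatinine of ≥ 4.0 mg/dL (≥ 354 mmol/L) with an acute increase of at least 0.5 mg/dL (44 mmol/L".

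On measurement, Protocol Section 6.6, Table 1 and Appendix II (Section 13.2) require a blood count and NT-proBNP at baseline and NT-proBNP at 6 months. No blood test is listed at discharge or 30 days, and urine output is not listed at all. Under Other Evaluations, Section 6.6 says: "The investigative team should follow their standard practices for assessment of suspected myocardial infarction, acute kidney injury, neurological events".

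On analysis, the CEC adjudicates events that investigators report (Protocol Section 7.7). The SAP applies Kaplan-Meier methods in the Attempted Implant set (Section 7.9.1) and censors a subject without an event at the last visit, assessment or event (Section 7.2).

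**The concern.** There are two separate problems.

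First, the definition gives each absolute creatinine threshold twice, with values that cannot both be right, and does the same for the stage 2 relative criterion. This is the text that adjudicators are told to apply.

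Second, an endpoint defined by change from baseline needs a baseline and a later value, and the schedule requires neither. A small creatinine rise with normal urine output is seen only if someone measures it. The CEC cannot recover a case that was never tested, and the Kaplan-Meier estimate treats a never-tested subject exactly like one who tested negative. SAP Section 7.4 intends the reported number of subjects to let a reader judge missing data. For AKI that number would not show who lacked a creatinine.

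What is at stake is the second primary objective (Protocol Section 4.1): estimating event rates for endpoints that pivotal studies might use. An AKI rate that partly reflects testing habits at up to 25 sites is a weak input to that.

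**Working it through.** **1. Units.** The inputs are the three pairs in Section 13.8.1. The documents give no molar mass, so creatinine at 113.12 g/mol is an assumption (range tried: 113.0 to 113.2). Formula: mmol/L = (mg/dL × 10) / molar mass.

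| mg/dL | Converted | Stated | Stated / converted | Stated value back in mg/dL |
|---|---|---|---|---|
| 0.3 | 0.0265 mmol/L = 26.5 µmol/L | 26.4 mmol/L | 995 | 299 |
| 4.0 | 0.354 mmol/L = 353.6 µmol/L | 354 mmol/L | 1001 | 4004 |
| 0.5 | 0.0442 mmol/L = 44.2 µmol/L | 44 mmol/L | 995 | 498 |

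Over the molar-mass range the ratios run from 994 to 1002. The stated figures do not reproduce as mmol/L. As µmol/L all three reproduce within 0.6%.

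A check that assumes no molar mass is to ask what each pair implies: (mg/dL × 10) / (mmol/L). This gives 3/26.4 = 0.114, 40/354 = 0.113 and 5/44 = 0.114 g/mol, which no molecule can have. Read as µmol/L, the pairs imply 113.0 to 113.6 g/mol.

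**2. Effect if the SI figure alone were applied.** No creatinine rise could meet it, so stage 1 would rest on the 1.5-fold rule or urine output. The two creatinine rules coincide where 0.5 × baseline = 0.3, that is, at a baseline of 0.6 mg/dL. Above that, the absolute rule is the easier one. At a baseline of 1.0 mg/dL the rise needed would go from 0.3 to 0.5 mg/dL; at 1.5, from 0.3 to 0.75 mg/dL.

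**3. Stage 2.** From a baseline of 1.0 mg/dL, 200%-299% means a value of 2.00 to 2.99 mg/dL. A 2.0%-2.99% increase means 1.02 to about 1.03 mg/dL. This slip, read literally, would raise the count, so the two errors in the definition point in opposite directions.

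**4. Ascertainment.** The sequence is: no creatinine scheduled (6.6, Table 1, 13.2); suspected AKI left to site practice (6.6); only investigator-reported events reach the CEC (7.7); no reported event means event-free until last contact (SAP 7.2). Incomplete testing can miss true cases but cannot add any, so any bias from this source is downward. Its size would need a true AKI rate and a detection fraction, and the documents give neither.

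**5. Time points.** With the definition closed at day 7 after the procedure, the Kaplan-Meier curve has no steps after that. For subjects whose only procedure falls on Day 0, the 30-day and 6-month estimates both equal the 7-day estimate.

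**6. Why restricting the denominator is not a remedy by itself.** Assume a true rate of 10%, with 90% of AKI cases tested and 50% of other subjects tested. The fraction tested is 0.10 × 0.90 + 0.90 × 0.50 = 0.54. The rate over all subjects is 9%; the rate among tested subjects is 0.09/0.54 = 16.7%. If 25% to 90% of the others are tested, the rate among tested subjects runs from 0.09/0.315 = 28.6% down to 0.09/0.90 = 10%. All of these inputs are assumed; they show direction only.

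**The case against.** The strongest reply is that the unit slip is editorial. Each mmol/L figure follows a usable mg/dL threshold in parentheses, the relative and urine-output criteria do not depend on the unit, coding is central, and no adjudicator would apply a threshold near 299 mg/dL. The mmol/L could even be a rendering fault in the circulated file, although the glossary prints µg correctly. Most of this stands as to effect: the slip lowers the count only if someone applies the SI figure literally. It does not excuse leaving contradictory thresholds in the adjudication text. The sponsor has already corrected a cited range elsewhere in the same appendix (footnote 12, Section 13.8.3).

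The second reply is that renal values will exist anyway:

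- GFR below 30 mL/min is an exclusion (Section 6.2.2).
- Labs are named among study-related testing (Section 6.10, footnote 5), and standard-of-care lab work may serve as a required baseline test (Figure 2 caption, Section 6.5).
- Abnormal laboratory findings fall within the adverse event definition (Table 2), all adverse events are reportable up to the 6-month visit (Section 7.2), and a creatinine rise is not on the exempt list (Table 3).

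This is fair, and it means many subjects may be tested. But the GFR value has no stated method or date and supplies nothing after the procedure, and the plan neither requires nor counts routine values.

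Third, AKI is not among the key endpoints (Protocol Synopsis; SAP Section 4), and the study is descriptive. That limits the weight of the point.

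**Conclusion.** The point holds in two parts. The definition contradicts itself: the SI thresholds are about 1000 times too large, a finding that does not depend on the exact molar mass, and stage 2 carries two incompatible relative criteria. The plan also does not schedule the measurement on which the creatinine criteria depend, so AKI may be under-ascertained and inconsistently classified across sites.

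A reader might go further and infer that AKI cannot be measured at all, or that it will certainly be under-counted. The documents do not support that. The mg/dL, relative and urine-output criteria stand beside the SI figures, the stage 2 slip would push the count up, and routine care may supply many values. Nor does the plan say that creatinine is measured only on suspicion. It leaves suspected cases to site practice and is silent on routine testing. No figure for the under-count can be given.

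The identical 30-day and 6-month rates are redundant, not wrong. The change is worth making because event-rate estimation is a primary objective and the remedy is cheap.

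**What to change.** 1. In Section 13.8.1, change the three SI thresholds from mmol/L to µmol/L, and the stage 2 parenthesis to 2.0-2.99 × baseline. This costs wording only.
2. In Section 6.6 and Table 1, add a serum creatinine at baseline and one post-procedure value before discharge, within 7 days, accepting values already drawn for routine care. This costs one chemistry value and one CRF field at each of two existing visits.
3. Once item 2 is in place, keep the Kaplan-Meier analysis in the Attempted Implant set. Report AKI at 7 days, noting that the 30-day and 6-month estimates are the same. State how many subjects lack paired creatinine values. Give the rate among assessed subjects only as a sensitivity analysis, and let it still count AKI met by urine output. This costs wording in SAP Section 7.9.1 and one extra table line. It should not be adopted without item 2, because a denominator limited to tested subjects can bias the rate upward when testing follows suspicion.
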